13.2. Data Analysis

A detailed description of the statistical methods will be contained in the Statistical Analysis Plan (SAP). Any change to the data analysis methods described in this section and/or the SAP will require an amendment only if it changes a principal feature of the study description. Any other changes to the data analysis methods will be described and justified in the Final Report or publication.

Based on the clinical practice in the opioid used and number of subjects enrolled per centre/country, an investigation of centre/country effect will be investigated including an independent variable for centres/country in the model as well as summary statistics if needed.

The choice of the imputation method for missing data will depend on the pattern of the missingdata and the type of the imputed variable.

The primary analysis will be performed on all subjects enrolled in the study and monitored with the Capnostream monitor and include all clinical outcomes that occur within the monitoring period(s) as for study design.

It is anticipated that SAS (SAS Institute Inc., Cary, NC, USA) will be used to perform all statistical analyses. Statistical tests will be based on a two-sided significance level of 0.05, and interaction effects will be evaluated at a significance level of 0.10. No adjustments for multiple comparisons will be performed. Additional exploratory analyses will be conducted as deemed appropriate.

The statistics above will be calculated by means of a GEE model as appropriate in order to take into account multiple events per subject and they will be reported together with the interval confidence (IC).

All assumptions for regression models will be assessed by viewing plots of the residual values.

Descriptive statistics will be used to summarize subject characteristics. This will include mean, standard deviation, median, minimum, and maximum for continuous variables, and counts and percentages for categorical variables. To compare subjects with and without the outcome, all categorical variables will be analyzed with the Chi-square test or the Fisher exact test or Cochran-Mantel-Haenszel test for trend for ordinal variables with 3 or more categories, as appropriate. Continuous variable parameter comparisons will be performed using t-test or Wilcoxon test according to the normal or non-normal distribution.

13.3. Primary Endpoint

At the end of data collection all subjects enrolled will be randomly assigned to the derivation set and the validation set at a ratio of 2 to 1. According to the outcome of the planned RD event rate monitoring, there could be the possibility to use the overall population as the derivation cohort. The validation sets will be performed using a bootstrapping method. A detailed description of the bootstrap method will be

Version 3.0, 29 Nov 2016

PRODIGY CIP

reported in the Statistical Analysis Plan (SAP). Bivariate odds ratios (ORs) and 95% confidence intervals (95% CIs) will be estimated. The possibility of collinearity between categorical variables will be also tested. The logistic regression model will be performed using a backward stepwise selection procedure in which the presence of event will be the dependent variable. Independent predictors will be entered into the model if a significant association, defined as $p \le 0.05$, will be identified from bivariate analysis and, to avoid over-fitted and unstable model the correlation coefficient between them should be less than 0.25.

The predictive risk score for RD will be calculated by multiplying each b coefficient (from the multivariate model by 10 and rounding to the nearest integer. The integers will then be added together to produce an overall RD risk score for each subject. The resulting continuous distribution of total risk scores across all subjects in the derivation set will be then stratified into 3 categories of points that grouped subjects according to the level of risk (low, medium and high risks). Model prediction performance will be assessed using calibration (the agreement between predicted and observed outcome) and discrimination (the ability to separate subjects with and without the outcome) and the R2 will be reported as an overall measure for discrimination and calibration. The Sensitivity and Specificity and the receiver-operating characteristic (ROC) curves will be used to visualize the overall accuracy of the model. The discriminatory performance of the model will be validated by comparing the ROC curve analysis in the derivation set with that in the validation set.

13.4. Secondary Endpoints

Comparisons on all categorical variables will be done using the Chi-square test or the Fisher exact test or Cochran-Mantel-Haenszel test for trend for ordinal variables with 3 or more categories, as appropriate. Continuous variable parameter comparisons will be performed using t-test or Wilcoxon test according to the normal or non-normal distribution.

The rate of events will be computed and reported separately for each group, together with their 95% confidence intervals. Rates will be then compared by means of either a mixed Poisson model or a negative binomial regression model (if overdispersion is present).

The Sensitivity and Specificity, Positve predictive value (PPV) and negative predictive value (NPV), and the ROC curves will be used to visualize the accuracy of the IPI algorithms at different cutoffs in predicting episodes.

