5.1.2. Secondary Objective(s)

The study secondary objectives are as follows:

- 1. To compare subjects that will develop RD versus subjects that will not develop RD (in terms of parameters additional to those needed for primary objective, see Section 5.2.2 for details).
- 2. To characterize the predictive values of etCO₂, RR, SpO₂ and the IPI in predicting RD and ORADE.
- 3. To measure health care utilization costs during the study period.

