5.2.2. Secondary Endpoint(s)

- 1. RD risk subjects versus no-risk subjects will be compared in terms of:
 - Incidence of AE's and actions taken.
 - Healthcare resource utilization (including hospital length of stay, 30 days readmission rate and primary diagnosis upon readmission).
 - Subject mortality at 30 days.
- 2. The predictive value (sensitivity, specificity, etc.) of etCO2, RR, SpO2, and IPI will be correlated with the occurrence of RD and ORADE.
- 3. Cost associated with events and actions taken will be estimated retrospectively using standard cost data from different countries.

6. Study Design

PRODIGY is a prospective, post-market interventional, multi-center, international cohort study.

A derivation cohort will be used to derive the risk assessment tool. An internal validation cohort will be used for evaluating the prognostic value of the score for the prediction of RD. Capnography and pulse oximetry monitoring device data will be collected as well as clinical data related to respiratory depression. Subjects will be monitored per standard of care. Enrollment at any single site will be limited to 20% (approximately 330 subjects) to ensure poolability of the data across sites and reduce potential bias. Additional methods incorporated to minimize potential bias include the following:

- Systematic identification of potential subjects via screening
- Both surgical and non-surgical candidates are eligible as event rates may vary
- Adjudication of RD events by an independent review committee
- Diverse geographical site representation to account for difference in practice

Version 3.0, 29 Nov 2016

PRODIGY CIP

- Standard procedures and data collection requirements with a common electronic database for all sites
- Provision of product for all study subjects

Foreseeable factors that may compromise the outcome of the study include lack of enrollment or the lack of respiratory depression events.

Approximately 1650 subjects will be enrolled in up to 16 centers from the United States (US), Europe and Asia. Geographic distribution of sites is anticipated as 8 sites (50%) in the US, 5 (30%) in Europe and 3 (20%) in Asia. Additional locations may be added during the course of the study.

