7.10.2.1 Secondary endpoint#1

The secondary objective#1 will be evaluated comparing subjects that will develop RD versus patients that will not develop RD in terms of:

- Incidence of AE and actions taken.
- Healthcare resource utilization (including hospital length of stay, 30 days readmission rate and primary diagnosis upon readmission).
- Subject mortality at 30 days.

This secondary objective will be explained in the Health Economic Analysis Plan (HEAP).

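### Neither the protocol nor the SAP pre-specifies adjustment when comparing stay, readmission and death between RD and no-RD subjects, and the protocol names two different pairs of groups

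*Protocol*

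**What the plan says.** Protocol 13.4 covers the secondary endpoints by type of variable. For categorical outcomes: "Comparisons on all categorical variables will be done using the Chi-square test or the Fisher exact test", with a Cochran-Mantel-Haenszel trend test for ordered categories. For continuous outcomes: "Continuous variable parameter comparisons will be performed using t-test or Wilcoxon test according to the normal or non-normal distribution". For event rates: "Rates will be then compared by means of either a mixed Poisson model or a negative binomial regression model (if overdispersion is present". None of these lists a patient covariate.

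Protocol 13.2 has one general covariate provision: "an investigation of centre/country effect will be investigated including an independent variable for centres/country in the model". SAP 7.3 repeats it. It concerns site and country, not patient characteristics.

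SAP 7.10.2.1 lists the outcomes (adverse events and actions taken, length of stay, 30-day readmission and its diagnosis, 30-day mortality), names no test or model, and states: "This secondary objective will be explained in the Health Economic Analysis Plan (HEAP".

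The groups are described in three places:
- Protocol 5.1.2: "To compare subjects that will develop RD versus subjects that will not develop RD".
- Protocol 5.2.2: "RD risk subjects versus no-risk subjects will be compared in terms of".
- SAP 7.10.2.1: "comparing subjects that will develop RD versus patients that will not develop RD in terms of".

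**The concern.** The study rests on the premise that RD can be predicted from baseline characteristics. The 12 candidates in Protocol 13.1.1 include age over 65, major organ failure, cardiac disease, pulmonary disease, diabetes and recent high-risk surgery. If the primary objective succeeds, the two groups in secondary endpoint 1 will differ on some of these factors. Several of them plausibly also affect stay, readmission and death whether or not RD occurs; the documents do not say this, so it is an assumption.

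A crude difference then mixes any effect of RD with case-mix. The protocol says the tool may guide who could benefit from capnography (4.2), and the costs of events and actions form a linked endpoint (5.2.2). A crude difference could therefore be taken as the clinical or economic consequence of RD. With no multiplicity adjustment planned, nominally significant results would stand as they are.

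The wording of the groups matters separately. Observed RD and predicted risk of RD are different exposures and answer different questions.

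**Working it through.** **Plan's own figures.** Protocol 13.1: 10 events per variable × 12 variables / 0.12 = 1000 for derivation; 1000 × 3/2 = 1500 in total; 1500 × 1.10 = 1650. This reproduces the stated sample size. At 12% RD, 1500 evaluable subjects give 0.12 × 1500 = 180 with RD and 1320 without. Neither document gives an effect size or power for the secondary comparisons, so no stated figure is in dispute here.

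Everything below is illustration. Only the 12% and the 180 versus 1320 come from the plan. In every scenario RD has no effect on outcome once the baseline factors are known.

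**A. One shared risk score, death.** Let x be standard normal, logit P(RD) = a + bx and logit P(death) = a′ + b′x. Intercepts are set to give 12% RD and 2% mortality (assumed); slopes give the same c-statistic for both outcomes (assumed 0.65 to 0.75). Death risk with RD is E[P(RD)·P(death)]/0.12; without RD it is E[(1 − P(RD))·P(death)]/0.88.

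| c | Death risk, RD | Death risk, no RD | Crude OR |
|---|---|---|---|
| 0.65 | 2.56% | 1.92% | 1.34 |
| 0.70 | 3.09% | 1.85% | 1.69 |
| 0.75 | 3.90% | 1.74% | 2.29 |

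At c = 0.70: (0.0309/0.9691)/(0.0185/0.9815) = 1.69. That is about 5.6 deaths among 180 (180 × 0.0309) against about 24 among 1320 (1320 × 0.0185), so the estimate would be very imprecise. A two-proportion z-test would reject in about a quarter of such studies.

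**B. Same score, length of stay.** Let log stay correlate r with x (assumed 0.1 to 0.4). The crude difference in SD units is r × the difference in mean score, which is 0.536, 0.718 and 0.903 at c = 0.65, 0.70 and 0.75. The standard error is √(1/180 + 1/1320) = 0.0795. The two-sided rejection probability at 0.05 is 1 − Φ(1.96 − δ/0.0795) + Φ(−1.96 − δ/0.0795).
- c = 0.65, r = 0.1: δ = 0.054, rejection 10%.
- c = 0.65, r = 0.2: δ = 0.107, rejection 27%.
- c = 0.70, r = 0.2: δ = 0.144, rejection 44%.
- c = 0.75, r = 0.4: δ = 0.361, rejection over 99%.

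**C. A single binary confounder.** Assume prevalence of 40% without RD and 50–70% with RD, a factor–outcome OR of 2–3, and a base rate of 10% (readmission) or 2% (death). Worked case: readmission, OR 3, 70% prevalence with RD. Risk with the factor is (0.1/0.9 × 3)/(1 + 0.1/0.9 × 3) = 0.25. Without RD: 0.10 + 0.15 × 0.4 = 0.160. With RD: 0.10 + 0.15 × 0.7 = 0.205. Crude OR = (0.205/0.795)/(0.160/0.840) = 1.35.

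Over the whole grid the crude OR is 1.07 to 1.35. The crude test rejects in 6.5–34% of studies for readmission and 5.8–15% for death. For stay, a factor that shifts the mean by 0.25–1.0 SD gives a crude difference of 0.025–0.30 SD and 6–97% rejection. With so few deaths, the normal approximation for mortality is rough.

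**D. The groups.** Protocol 5.1.2 and SAP 7.10.2.1 divide subjects by whether RD occurred. Read literally, Protocol 5.2.2 divides them by risk. No two-level risk grouping is defined: Protocol 13.3 splits the score into low, medium and high, and SAP 7.10.1.1 allows tertiles, quintiles or optimal cut-offs.

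**The case against.** The strongest point is that a reader might infer that these outcomes will be analysed only by unadjusted tests. The documents do not establish that. The SAP hands this endpoint to the health-economic plan, which may adjust. Readmission is listed as a rate, so it may fall under the Poisson or negative binomial model, which could carry covariates. A centre/country term is foreseen and exploratory analyses are allowed. All this stands against the stronger reading, but none of it names a patient risk factor, so the gap in the protocol and SAP remains.

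Second, the documents only compare the groups; they do not attribute stay or death to RD. A crude comparison is legitimate as description. That is right, but neither document labels it descriptive.

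Third, the size is assumption-driven. One score driving both RD and outcome is close to the strongest confounding possible at a given c, and a single binary factor gives much smaller distortion. A reader might infer that case-mix will certainly produce longer stay and higher mortality in the RD group; the documents do not support that certainty.

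Fourth, adjustment has its own traps. Opioid dose and sedatives are among the 12 factors, and Protocol 9.4 also records medications during monitoring, so careless adjustment could use values that follow the RD episode. The stepwise score may also drop confounders. Both points stand and shape the fix.

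Fifth, the group conflict may be loose drafting: Protocol 5.1.2 states observed RD and points to 5.2.2 for the parameters, and the later SAP uses observed RD throughout. That is probably so, but the texts still need to agree.

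**Conclusion.** The point holds in a limited form. For secondary endpoint 1 the only methods named in the protocol are unadjusted two-group tests, or a rate model without named covariates. The SAP names none and refers to a plan that was not available. No adjustment for patient risk factors is therefore pre-specified in the protocol or SAP, and crude differences cannot be attributed to RD.

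The size cannot be fixed from the documents. On the assumptions above, spurious crude odds ratios for death run from 1.34 to 2.29 under near-maximal confounding, and odds ratios for readmission or death are about 1.07 to 1.35 for one binary factor. Spurious significance for length of stay runs from 10% to over 99% under the shared score. Every scenario exceeds the nominal 5%, some only slightly.

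Protocol 5.2.2 also conflicts with Protocol 5.1.2 and SAP 7.10.2.1 on the groups. This is a secondary endpoint and the derivation of the score is unaffected, so the change is advisable rather than essential.

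**What to change.** In Protocol 13.4 and in SAP 7.10.2.1 or the health-economic plan:

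- Keep the crude tests and label them descriptive.
- Add a pre-specified regression of each outcome on committee-adjudicated RD, adjusted for country and the protocol's 12 risk factors as measured before the start of monitoring: logistic for readmission, log-link or negative binomial for length of stay.
- For 30-day death, where events will be few, use a penalised model or a single baseline risk summary built from all pre-monitoring candidate factors, not only those kept by stepwise selection.
- Reword Protocol 5.2.2 so that it compares subjects who develop RD with subjects who do not, matching Protocol 5.1.2 and the SAP.

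If the health-economic plan already contains such models, a cross-reference in the SAP naming them and their covariates would be enough for the modelling part. The cost is some wording and a few extra models: medical history, demographics, surgery and medications are already collected. The downside is that adjusted differences will probably be smaller and less precise.

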Ethical Committee / Institutional Review Board	EC / IRB	Any board, committee, or other group formally designated by an institution to review, to approve the initiation of, and to conduct periodic review of, biomedical research involving human subjects. The primary purpose of such review is to assure the protection of the rights and welfare of the human subjects.
End Tidal CO2	etCO ₂	The numeric partial pressure of the maximum value of carbon dioxide in the exhaled breath over the last 20 seconds. The etCO ₂ numeric value is updated once a second.
Emergency Room	ER	Medical treatment facility specializing in emergency medicine, the acute care of patients who present

Version 3.0, 29 Nov 2016

Term	Abbreviation	Definition
		without prior appointment; either by their own means or by that of an ambulance.
Fractional inspired carbon dioxide	FiCO ₂	The numeric partial pressure of carbon dioxide present during inhalation.
Intensive Care Unit	ICU	Acute care with 24 hour coverage. Patients may be directly transferred direct from the OR to the ICU or via the PACU.
Integrated Pulmonary Index™	IPI	The Integrated Pulmonary Index (IPI) is a composite index of $etCO_2$, SpO_2 , RR and PR that is intended to indicate changes in physiological status as indicated by the monitored variables and cleared by FDA (K082268) in 2009.
Pulse Rate	PR	Pulsatile cycle in beats per minute via pulse oximeter technology.
Pulse Oximetry	SpO₂	Depends on pulsatile blood flow and measures only the oxygemoglobin in arterial blood as it leaves the heart.
Remote Data Capture	RDC	An interface that allows site users at sites to enter data directly into the study database via a web interface. RDC is an example of Electronic Data Capture method or EDC.
Respiratory Compromise	RC	Respiratory compromise consists of respiratory insufficiency, compromise, distress, arrest, and failure. Respiratory Compromise is a state in which there is a high likelihood of decompensation into respiratory insufficiency, respiratory failure or death, but in which specific interventions (enhanced monitoring and/or therapies) might prevent or mitigate decompensation.
Respiratory Depression	RD	Respiratory depression is a clinical diagnosis made after reviewing monitoring data in conjunction with the clinical data and consistent with accepted pathophysiologic mechanisms.
Respiratory Opioid- Related Adverse Events (ORADE)	rORADE	An episode of respiratory compromise that is related to opioid analgesia therapy.

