7.8 Treatment Characteristics

Extent of exposure in the population is characterized according to the duration of opioid therapy with monitoring.

Duration of **Opioid Exposure before Monitoring** will be measured in minutes from the start of the Opioid therapy and the starting of the Monitoring: Duration of Opioid Exposure before Monitoring exposure (minutes) = (Start monitoring date/time – Start Opioid therapy date/time). The extent of Opioid Exposure before Monitoring will be presented in a summary table and supporting data listing.

Table 21 – Opioid Exposure before monitoring - FAS, MFAS, PRDPS

Duration of **Monitoring Exposure** will be measured in minutes from the start of the monitoring through and including the time of monitoring end: Duration of monitoring exposure (minutes) = (End monitoring date/time – Start monitoring date/time). Extent of Monitoring exposure will be presented in a summary table and supporting data listing.

Table 22 – Monitoring Exposure - FAS, MFAS, PRDPS

The monitoring exposure will be also described in terms of the quality check, reporting EtCO2 and SpO2 gap overall and during the first 8 hours.

Duration of **Study Exposure** will be measured in days starting from the point of enrollment (informed consent completed and inclusion/exclusion criteria confirmed per the screening evaluation) through and including the time of study exit: Duration of study exposure (days) = (Study Exit date – date of enrollment). Extent of study exposure will be presented in a summary table and supporting data listing.

Table 23 - Study Exposure - FAS, MFAS, PRDPS

Descriptive statistics will be used to summarize study device information for FAS:

Table 24 - Study Device Information - FAS

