7.10.2.2 Secondary endpoint#2

The secondary objective#2 will characterize the predictive values of etCO₂, RR, SpO₂ and the IPI⁵ in predicting rORADE. To evaluate the predictive values of the Capnostream monitoring parameters for rORADE, the Sensitivity, Specificity, PPV and NPV will be calculated. rORADE events will be considered the Gold standard and the CS20p monitoring parameters as the measurement to be tested. The population used for this endpoint is PRDPS adjudicated as RD. All Clinical Events occurring during not monitored period will be reported but excluded from the table below. For each RD adjudicated by the CEC, the Capnostream monitoring will be checked if any of the parameter meets at least once the thresholds (RR \leq 6 breaths for \geq 3 minutes, SpO₂ \leq 85% for \geq 3 minutes, EtCO₂ \geq 60 mmHg for \geq 3 minutes or IPI < 3,4,5,6). The table below shows the distribution of the true and false positive and negative for each monitored parameter:

Test		Gold Standard		
Monitoring Parameter		ORADEs/RDs		
RR ≤ 5 breaths for ≥ 3 minutes		YES	NO	Tot
	YES	TP	FP	TP+FP
	NO	FN	TN	FN+TN
	Tot	TP+FN	FP+TN	N
Monitoring Parameter		ORADEs/RDs		
SpO2 ≤ 85% for ≥ 3 minutes		YES	NO	Tot
	YES	TP	FP	TP+FP
	NO	FN	TN	FN+TN
	Tot	TP+FN	FP+TN	N
Monitoring Parameter		ORADEs/RDs		
etCO2 ≤ 15 or ≥ 60 mmHg for ≥ 3 minutes		YES	NO	Tot
	YES	TP	FP	TP+FP
	NO	FN	TN	FN+TN
	Tot	TP+FN	FP+TN	N
Monitoring Parameter		ORADEs/RDs		
IPI <3		YES	NO	Tot
	YES	TP	FP	TP+FP
	NO	FN	TN	FN+TN
	Tot	TP+FN	FP+TN	N
IPI <4		YES	NO	Tot
	YES	TP	FP	TP+FP
	NO	FN	TN	FN+TN
	Tot	TP+FN	FP+TN	N
IPI <5		YES	NO	Tot
	YES	TP	FP	TP+FP
	NO	FN	TN	FN+TN
	Tot	TP+FN	FP+TN	N
IPI <6		YES	NO	Tot
	YES	TP	FP	TP+FP
	NO	FN	TN	FN+TN
	Tot	TP+FN	FP+TN	N
Monitoring Parameter		ORADEs/RDs		
Any Monitoring Parameter RR ≤ 6 breaths for ≥ 3 min or SpO2 ≤ 85% for ≥ 3 min or EtCO2 ≥ 60 mmHg for ≥ 3 min or IPI < 3,4,5,6		YES	NO	Tot
	YES	TP	FP	TP+FP
	NO	FN	TN	FN+TN
	Tot	TP+FN	FP+TN	N

Where:

- N will be all RDs adjudicated by the CEC.
- TP= true positive are all rORADEs and parameter over/below the threshold.
- FN= false negative are all rORADEs but no parameter over/below the threshold.
- FP= false positive are all no rORADE but parameter over/below the threshold.
- TN=true negative are all no ORADEs and no parameter over/below the threshold.

Measure of the accuracy will be:

- Sensitivity: $\{TP/(TP+FN)\}$,
- Specificity: $\{TN/(FP+TN)\}$,
- Positive predictive value: $\{TP/(TP+FP)\}$,

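### SAP 7.10.2.2 has no not-evaluable category, so an RD with no valid signal on a channel is scored as a negative test for that channel, by an amount that differs between etCO2, RR, SpO2 and IPI

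*Protocol*

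**What the plan says.** The scoring rule is in SAP 7.10.2.2. Protocol 13.4 only names the accuracy measures and states that "the ROC curves will be used to visualize the accuracy of the IPI algorithms".

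- **Denominator, the same in every table:** "N will be all RDs adjudicated by the CEC".
- **Positive test:** "the Capnostream monitoring will be checked if any of the parameter meets at least once the thresholds".
- **Negative test:** "FN= false negative are all rORADEs but no parameter over/below the threshold", and "TN=true negative are all no ORADEs and no parameter over/below the threshold". Neither definition requires the channel to have been recording.
- **Only exclusion:** "All Clinical Events occurring during not monitored period will be reported but excluded from the table below". It does not mention a gap on one channel while the monitor is running, or RDs that were detected from device data and not reported as clinical events.

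Gaps are expected. SAP 7.8 describes monitoring quality by "reporting EtCO2 and SpO2 gap overall and during the first 8 hours", but does not link this to the accuracy tables. SAP 7.1.3 keeps patients with interrupted monitoring in the MFAS, from which the PRDPS is drawn. SAP 7.4 has no rule for device-channel gaps. SAP 9.4 sends clinical events to the committee whether or not the device shows an episode.

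On IPI, the Protocol glossary says "The Integrated Pulmonary Index (IPI) is a composite index of" etCO2, SpO2, RR and PR. RR is counted from the CO2 waveform and PR comes from the oximeter, so the four inputs come from two sensors.

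**The concern.** An RD that a channel could not have registered is different from one it recorded without a crossing. The tables put both in the same row. Suppose the finger sensor is working, the cannula is off, and SpO2 triggers an RD. The patient is being monitored, so the exclusion does not clearly apply, yet the event is counted as negative for etCO2 and RR. It becomes a false negative if it is an rORADE and a true negative otherwise.

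Displacement may go unnoticed for some time, because Protocol 9.6 silences the alarms, hides the screen and relies on a periodic check of fit.

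Table 27 sets the parameters side by side. If the share of untested events differs by column, the columns differ partly through sensor adherence and not only through accuracy. rORADEs may be few, so a handful of such events could move a sensitivity visibly.

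**Working it through.** **1. Size of the tables.** The plan states no figure for this endpoint, but its sample size sets the scale. The three component incidences give 1 − (0.986 × 0.90 × 0.99) = 12.1%, close to the planned 12%. Then 12 × 10 = 120 events; 120/0.12 = 1000; × 3/2 = 1500; × 1.10 = 1650, which reproduces the plan. Expected subjects with RD: 0.12 × 1500 = 180. The number of rORADEs is not given. As an assumed proxy, the 0.3% to 3.4% intervention rate in Protocol 4.1 gives 0.003 × 1500 = 4.5 to 0.034 × 1500 = 51. One event moved from true positive to false negative then costs between 1/51 = 2 and about 1/5 = 20 percentage points of sensitivity.

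**2. Formulas.** Let g be the share of events with no valid reading on a channel in the whole window, stored as blank and independent of rORADE status.

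- Se_obs = Se(1−g)
- Sp_obs = 1 − (1−Sp)(1−g) = Sp + g(1−Sp)
- PPV is unchanged, because true and false positives both shrink by (1−g). NPV falls.
- If IPI needs all its inputs, g_IPI is at least the larger of the two sensor gaps. With independent gaps, g_IPI = 1 − (1−g_CO2)(1−g_SpO2).

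**3. Results.** Gap rates, true sensitivity 0.80 and true specificity 0.60 are all assumptions. Cells show sensitivity/specificity.

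| CO2-line gap | SpO2 gap | IPI gap | etCO2 | SpO2 | IPI |
|---|---|---|---|---|---|
| 5% | 5% | 9.8% | 0.76/0.62 | 0.76/0.62 | 0.72/0.64 |
| 10% | 5% | 14.5% | 0.72/0.64 | 0.76/0.62 | 0.68/0.66 |
| 20% | 5% | 24% | 0.64/0.68 | 0.76/0.62 | 0.61/0.70 |
| 30% | 10% | 37% | 0.56/0.72 | 0.72/0.64 | 0.50/0.75 |
| 5% | 20% | 24% | 0.76/0.62 | 0.64/0.68 | 0.61/0.70 |

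For example, in the third row the IPI gap is 1 − 0.80 × 0.95 = 0.24, sensitivity 0.80 × 0.76 = 0.61 and specificity 1 − 0.40 × 0.76 = 0.70. With 51 rORADEs among 180 RDs, PPV stays at 0.442 throughout. NPV for IPI in that row falls from 0.884 to 0.818.

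**4. Gaps related to event status.** A 20% gap only among rORADEs gives 0.64/0.60. A 20% gap only among the other RDs gives 0.80/0.68.

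**5. If a displaced line records low or zero values instead of blanks.** The event is then scored as crossed, so Se_obs = Se + g(1−Se) and Sp_obs = Sp(1−g). At g = 20% these are 0.80 + 0.20 × 0.20 = 0.84 and 0.60 × 0.80 = 0.48. RR would cross under either limit printed in SAP 7.10.2.2 (5 or 6 breaths). etCO2 would cross under the limits in its table, which include 15 mmHg or less, but not under the running text, which has only the upper limit.

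**6. After correction.** With not-evaluable events removed per channel and gaps independent of event status, every column returns to 0.80/0.60. The cost is in numbers: at 20% and 5% gaps, 180 × 0.80 = 144 RDs remain for etCO2, 180 × 0.95 = 171 for SpO2 and 180 × 0.76 = 137 for IPI.

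**The case against.** The SAP does not state that a missing reading counts as negative. That follows from its definitions, its fixed denominator and its silence on channel gaps. The exclusion for unmonitored periods could be read to include a lost channel, and it covers clinical events, which is where rORADEs arise. This stands as a point about wording, but the term is undefined and device-detected RDs fall outside the exclusion.

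One crossing is enough for a positive test, and SAP 9.3 extends each episode file 30 minutes either side. If that is the window used, only a gap lasting an hour or more leaves no reading. The assumed rates are therefore rates of whole-window loss, not of ordinary brief dropouts. This stands and limits the likely size.

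Counting a failed reading as a missed detection is a defensible measure of a monitor in ward use, and available-case tables are themselves biased if gaps relate to the event. This also stands. It is a reason to report both versions, not to leave the choice implicit.

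A reader might infer that the plan penalises etCO2 against SpO2. The documents do not support that: no gap rates are given, and the order reverses in the last row of the table. Nor do IPI gaps compound over four independent channels. With two sensors, the 20%/5% case gives 24%, not the 42% that four would give.

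**Conclusion.** The point holds as a gap in the scoring rule of SAP 7.10.2.2. Events with no usable signal on a channel have nowhere to go but the negative row. The misclassification differs by parameter, and for IPI it is at least as large as for either sensor if IPI needs all its inputs. On assumed gaps of 5% to 30%, a true sensitivity of 0.80 would be reported between 0.76 and 0.56 for a single sensor and between 0.72 and 0.50 for IPI, with specificity raised.

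This rests on gaps being stored as blanks, being independent of event status and covering the whole review window. The documents settle none of these, and do not say what IPI shows when an input is missing.

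A reader might infer that all the accuracy figures get worse, or that the direction is certain. Neither follows. Under the blank-gap assumption specificity is flattered and PPV is unchanged, and if a displaced line records low values the error runs the other way for RR, and for etCO2 under its low limit. No formal ranking of parameters is planned, and the primary objective is not touched. It is worth correcting before the secondary endpoint is analysed.

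**What to change.** In SAP 7.10.2.2:

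1. State the review window for each event, and define evaluability per channel as a minimum share of artefact-free signal within it. Three valid minutes would be too weak a test in a window of an hour or more. Give IPI its own criterion, since its rule has no three-minute duration.
2. State how readings from a displaced line are recognised, so that low or zero artefacts do not count as crossings.
3. Extend the exclusion for unmonitored periods explicitly to single-channel gaps and to device-detected RDs.
4. Show the not-evaluable count in each column of Table 27, split by rORADE status.
5. Add one table restricted to events with all channels valid, for reading the parameters against each other.
6. Keep the all-events scoring as a sensitivity analysis, labelled as performance in use.

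The cost is SAP wording, a validity flag from device data already collected, and a little more programming. The downside is fewer events per column and wider intervals.
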